1. To evaluate whether “one stop” integrated health services delivered in a mobile unit, supported by peer navigation, compared to peer navigation to similar health services available at community-based agencies, the following endpoint(s) will be assessed:
 - a. The intervention improves use of MOUD at 52 weeks
 - Documented current use of MOUD: alive, retained, with biological evidence of MOUD (any detectable medications) at the week 52 visit and a MOUD prescription current at 52 weeks after enrollment or proof of current receipt of MOUD from a clinic that does not provide individual MOUD prescriptions (e.g., methadone clinics) at the week 52 visit
 - Documented use of MOUD during the study: a MOUD prescription documented during the 52 weeks of study follow-up or proof of current receipt of MOUD from a clinic that does not provide individual MOUD prescriptions (e.g., methadone clinics) during the 52 weeks of study follow-up
 - b. The intervention increases rates of viral suppression among people living with HIV at 26 and 52 weeks
 - Among participants living with HIV at enrollment: alive, retained, and virally suppressed (VL <200 copies/mL) at the week 26 and week 52 visits, separately.
 - c. The intervention increases use of PrEP among people without HIV at 26 and 52 weeks
 - Among participants without HIV at enrollment: alive, retained, HIV negative, with detectable PrEP drugs in DBS at the week 52 visit
 - Among participants without HIV at enrollment: alive, retained, HIV negative, with protective levels of PrEP drugs in DBS samples at the week 26 and 52 visits
 - d. The intervention decreases opioid and polysubstance use at 26 and 52 weeks
 - Alive, retained, and no opioids (natural or synthetic), stimulants (methamphetamine, cocaine) or benzodiazepines detected in urine samples at week 26 and 52 visits
 - e. The intervention decreases prevalence of bacterial STIs at 26 and 52 weeks
 - Alive, retained and no evidence of gonorrhea, chlamydia, or new or recurrent syphilis infection detected at the week 26 and 52 visits

- f. The intervention reduces the rate of fatal and non-fatal overdose events by 26 and 52 weeks,
 - Death, with overdose as cause
 - Self-report of non-fatal overdose, collected at week 26 and 52 visits
 - g. The intervention increases the proportion of participants with undetectable HCV RNA among those with chronic HCV infection at enrollment

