3.2 Statistical Analysis Issues

- **Missing Data:**
In anticipation of the potential for missing data in this unstable study population, a missing-data strategy has been built into the primary endpoints. A positive result for each endpoint is defined as being “alive, retained,” and meeting the MOUD, ART, or PrEP criteria at 26 weeks from enrollment. If the 26-week visit is missing for any individual, that individual is “not retained” at 26 weeks, and the 26-week result for that person will be considered “negative”.

Secondary endpoints are defined similarly. If missing data rates are higher than anticipated (over 15%) for primary or secondary endpoints, sensitivity analyses will be conducted to assess the impact of assuming missed visits represent negative outcomes.
- **Missing Start and Stop Dates:**
Start date:
 - If start date is completely missing, start date will not be imputed.
 - If year is present and month and day are missing, then set month and day to January 1 or date of enrollment whichever is later.
 - If year and day are present and month is missing, the set month to January or date of enrollment whichever is later.
 - If year and month are present and day is missing, set day to the 1st day of month or date of enrollment whichever is later.Stop date:
 - If end date is completely missing, end date will not be imputed.
 - If year is present and month and day are missing, then set month and day to December 31st or date of termination whichever is earlier.
 - If year and day are present and month is missing, set month to December or date of termination whichever is earlier.
 - If year and month are present and day is missing, set day to the last day of month.
- **Out of window visits:**
For each required study visit, there is an allowable visit window specifying on which study days (post-enrollment) the visit is “allowed” to be completed. The allowable visit windows are contiguous between week 26 and week 52 and do not overlap. Within each allowable visit window, there is a target visit window and study visits should ideally be conducted within this window. Further details about visit windows are defined at section 6.8 of the Protocol V2.0.

All data will be tabulated per the evaluation visit as recorded on the CRF even if the assessment is outside of the visit window. In data listings, actual visit dates will be presented alongside nominal visit types.

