These outcomes will be modeled and summarized using the same strategy as specified for the primary outcome in section 8 above.

- d) Decreases opioid and polysubstance use at 26 and 52 weeks

Outcome:

- Opioids (natural or synthetic) detected in urine samples for those retained at the week 26 and 52 visits (visits analyzed separately).
- Opioids (natural or synthetic) detected, along with stimulants (methamphetamine, cocaine), xylazine and/or benzodiazepines detected in urine samples at the week 26 and 52 visits (visits analyzed separately).

This objective will be analyzed only in those giving a urine sample at the respective visit (week 26 or week 52).

Opioids (natural or synthetic) include opiates, fentanyl and synthetic opioids.

Opiate detection includes 6-mam, codeine, dihydrocodeine, heroin, hydrocodone, hydromorphone, morphine, morphine glucuronide naloxone, and normorphine.

Fentanyl detection includes 4-ANPP, acetyl fentanyl, alfentanil, fentanyl, FIBF, furanyl fentanyl, methoxyacetyl fentanyl, norfentanyl, para-chlorofentanyl, para-fluorofentanyl, and valeryl fentanyl.

Synthetic Opioid detection includes isotonitazene, meperidine, metonitazene, noroxycodone, oxycodone, oxymorphone, tapentadol, tramadol, and U-47700.

Stimulant detection includes amphetamine, MDA, MDEA, MDMA, methamphetamine, methylphenidate, phentermine, benzoyllecgonine, cocaethylene, and cocaine.

Benzodiazepine detection includes alpha-hydroxyalprazolam, alprazolam, carisoprodol, chlordiazepoxide, clonazepam, diazepam, flurazepam, lorazepam, nordiazepam, oxazepam, and temazepam.

These outcomes will be modeled and summarized using the same strategy as specified for the primary outcome in section 8 above.

e) Decreases prevalence of bacterial STIs at 26 and 52 weeks

Outcome:

- Gonorrhea, chlamydia, or new or prevalent syphilis infection detected via local labs for those retained at the week 26 and 52 visits (visits analyzed separately).

This objective will be analyzed only in those giving a specimen and having a valid test result at the respective visit (week 26 or week 52).

Negative for syphilis, at any visit, is defined as a negative/not-detected non-treponemal test; or a positive non-treponemal test and a negative/not-detected treponemal test (this would be considered a false-positive test and thus considered negative for the visit).

Prevalent syphilis is defined as a positive non-treponemal test and a positive treponemal test, with a titer value $\geq 1:8$.

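### Secondary outcomes 1d (substance use) and 1e (bacterial STIs) have different denominators and different event criteria in Sections 2.2/3.2 and Section 10 of the SAP, and nothing says which governs.

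*SAP*

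**What the plan says.** **Section 2.2** makes each outcome a success composite. Substance use (1d): "Alive, retained, and no opioids (natural or synthetic), stimulants (methamphetamine, cocaine) or benzodiazepines detected in urine samples at week 26 and 52 visits". Bacterial STIs (1e): "Alive, retained and no evidence of gonorrhea, chlamydia, or new or recurrent syphilis infection detected at the week 26 and 52 visits".

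**Section 3.2** sets the missing-data rule. If the 26-week visit is missed, the participant is not retained and "the 26-week result for that person will be considered" negative, that is, a failure. It then adds: "Secondary endpoints are defined similarly". No exception is made for 1d or 1e. A sensitivity analysis of the missed-visit assumption is promised under this condition: "If missing data rates are higher than anticipated (over 15%) for primary or secondary endpoints". The analysis set in Section 3.1 is ITT: everyone enrolled except those inappropriately enrolled.

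**Section 10** turns both outcomes into detection events and narrows the denominator. For 1d: "This objective will be analyzed only in those giving a urine sample at the respective visit (week 26 or week 52"). For 1e: "This objective will be analyzed only in those giving a specimen and having a valid test result at the respective visit". The single drug composite becomes two events. One is any opioid detected. The other is "Opioids (natural or synthetic) detected, along with stimulants (methamphetamine, cocaine), xylazine and/or benzodiazepines detected in urine samples". For STIs, the syphilis component is new or prevalent infection, where prevalent means both tests positive with a titer of at least 1:8.

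**The concern.** The same named outcome has two sets of rules in one document. They differ in three respects: who is counted, what happens to participants without a result, and what counts as an event. The dead, the lost and the untested are all outside the Section 10 analysis, whereas the dead and the lost are failures under Sections 2.2 and 3.2.

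If retention differs by arm, the choice of denominator can create or remove an apparent arm effect. The study is unblinded and Section 3.2 itself anticipates missing data in an unstable population, so the choice should be fixed before results are seen. The criterion differences matter even if every participant attends and is tested.

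**Working it through.** The SAP gives no expected rate, power or sample size for 1d or 1e, so there is no stated figure to reproduce. The check sets the definitions side by side and then illustrates the denominator effect.

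**1. Drug criterion, by urine result at the visit**

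| Participant | Section 2.2 (with 3.2) | Section 10, opioids | Section 10, opioids plus another |
|---|---|---|---|
| Stimulant only | failure | no event | no event |
| Benzodiazepine only | failure | no event | no event |
| Opioid only | failure | event | no event |
| Opioid and xylazine only | failure, through the opioid | event | event |
| Retained, no urine | not stated | excluded | excluded |
| Missed visit or dead | failure | excluded | excluded |

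The first two rows show that the versions disagree among fully tested participants. Xylazine appears only in Section 10.

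**2. Syphilis criterion.** Section 2.2 uses new or recurrent infection, and the SAP never defines recurrent. Section 10 uses new or prevalent infection and defines both. On a plain reading, a participant with both tests positive and a titer of at least 1:8 that has persisted since enrollment is prevalent under Section 10 but neither new nor recurrent under Section 2.2.

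**3. Denominator effect.** Inputs, all assumed: the probability q of being STI-free among those tested, equal in both arms, and retention r by arm. Everyone retained is taken to be tested.

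- Sections 2.2/3.2: success in an arm = r × q, so the difference = q × (r_intervention − r_control).
- Section 10: difference = q − q = 0.

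| q | Retention, intervention vs control | Overall missing (equal arms) | Sections 2.2/3.2 | Section 10 |
|---|---|---|---|---|
| 0.90 | 90% vs 85% | 12.5% | 0.90 × 0.05 = 4.5 points | 0 |
| 0.90 | 85% vs 75% | 20% | 0.90 × 0.10 = 9 points (76.5% vs 67.5%) | 0 |
| 0.90 | 85% vs 85% | 15% | 0 | 0 |
| 0.10 | 85% vs 75% | 20% | 0.10 × 0.10 = 1 point | 0 |
| 0.20 | 85% vs 75% | 20% | 0.20 × 0.10 = 2 points | 0 |

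The last two rows stand for the drug outcome, assuming that few participants are negative for all listed drugs. If retention favours control, the signs reverse: 80% vs 90% with q = 0.90 gives −9 points.

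**4. Does the planned sensitivity analysis resolve it?** No. It examines the assumption that a missed visit is a failure. Section 10 does not make that assumption for 1d and 1e, so under Section 10 there is nothing for it to examine. No section requires both versions to be reported.

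**The case against.** **Section 10 is the operative text.** Section 2.2 lists objectives and endpoints, while Section 10 supplies the analyte lists, the titer cut-off, the denominators and the model. Its restriction is explicit and tied to each objective, whereas the sentence in Section 3.2 is general. A programmer would probably follow Section 10, and that may be what was intended. But this is an inference, because the SAP states no order of precedence. The change history lists both 2.2 and 10 as revised for v2.0, so neither can be set aside as leftover text. Within Section 10, the current-use outcome in 1a and the outcomes in 1b and 1c keep the alive-and-retained form, and the departure in 1d and 1e is not explained.

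**Prevalent may simply be the laboratory version of recurrent.** Possibly, but the words are not equivalent and the SAP does not link them. This is the weaker of the two criterion differences.

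**The composite should lead because it keeps the whole ITT set.** A reader might infer this, but the documents do not settle it. The stated objective for 1e is STI prevalence, and the illustration shows the composite giving 9 points when prevalence among those tested is identical. Sections 2.2 and 3.2 also leave a retained participant without a valid result uncoded, which Section 10 does settle. The tested-only version has its own weakness, since it conditions on an event after randomisation.

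**The numbers are unfavourable.** The 85% vs 75% case implies 20% missing, above the 15% that Section 3.2 treats as higher than anticipated. That is fair, and it is why the 90% vs 85% case is shown as well.

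**Conclusion.** The contradiction stands. Outcomes 1d and 1e are defined incompatibly in current SAP text, in denominator, in handling of missing results and in event criteria. The criterion differences depend on no assumption. The denominator effect depends on unequal retention: 4.5 points at 90% vs 85% and 9 points at 85% vs 75%, if 90% of those tested are STI-free in both arms. It is about 1 to 2 points for a drug-negative rate of 10% to 20% at 85% vs 75%. It is nil with equal retention and equal tested rates. All of these rates are assumptions.

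A reader might go further and infer that the two versions will point in opposite directions, or that the team will choose between them after seeing the data. Opposite signs are arithmetically possible. If 88% vs 90% (intervention vs control) are STI-free among those tested and retention is 85% vs 75%, Section 10 gives −2 points and Sections 2.2/3.2 give 0.748 − 0.675 = +7.3. But the SAP gives no rates that make this likely, and nothing in it indicates selective choice. Section 5 requires deviations from the plan to be described in the final report.

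Two of the eight arm-comparison sub-objectives (1a to 1h) are affected. The primary outcomes and the sample size are not. This should be fixed, but it does not threaten the trial's main conclusions.

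**What to change.** Before database lock, name one definition and one denominator for each of 1d and 1e, and align Sections 2.2, 3.2 and 10 to them. The text needs:

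- one drug list, with or without xylazine;
- one rule for the drug event, either any listed drug or an opioid plus another, and a statement of whether there are one or two outcomes;
- one syphilis criterion, with every term defined;
- a stated coding for retained participants with no urine or no valid test result;
- in Section 3.2, either an explicit exception for 1d and 1e or confirmation that the missed-visit rule applies to them.

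Which denominator leads is the sponsor's choice. Report the other as a labelled sensitivity analysis, with retention and specimen availability by arm beside it. The cost is SAP wording, an extra column in the secondary-outcome tables and a short table of retention and specimen counts. No new data are needed.

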5. GENERAL ANALYSIS METHODS

Participants characteristics at baseline will include the number of subjects with non-missing value (n), plus frequency and percentage for the categorical variables; and mean, median, standard deviation (SD), minimum (min), and maximum (max) for the continuous variables. Baseline is defined as Enrollment visit, except for data collected at screening and not at enrollment visit. For example, opioids data collected at screening visit will be considered as baseline data.

Any deviations from this statistical plan will be described in the final report. Primary and secondary outcomes will be limited to data collected within the allowable visit window for the week 26 and week 52 visits, respectively.

For all outcomes below, “retained” at 26 weeks is defined as having completed the 26-week visit within the allowable window of 126-308 days from enrollment, and “retained” at 52 weeks is defined as having completed the 52-week visit within the allowable window of 309-449 days from enrollment.

[figure not shown]
For MOUD outcomes, biological detection of Buprenorphine (or Norbuprenorphine or Buprenorphine Glucuronide) or Methadone (or EDDP) will be performed via laboratory analysis of plasma and urine samples. Detectable MOUD is defined as a value above the lower limit of quantitation (LLOQ) for any of the medications or metabolites mentioned above, in either plasma or urine.

For PrEP outcomes, the PrEP regimen tested (Truvada or Descovy in DBS, or CAB-LA in plasma) is determined based upon reported PrEP use. If there is no reported PrEP usage, the default regimen is Truvada. Detectable PrEP is defined as a value above the lower limit of quantitation (LLOQ) for the PrEP regimen tested.

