9.1 Adverse Events and Deaths

Adverse events (AEs) that study staff become aware of will be recorded in source documentation and will be assessed for seriousness. Non-serious AEs will not be reported in the study database and referrals for care will be provided as necessary. Only Serious adverse events (SAEs) will be reported in form of tables and listings categorized by system organ class, severity grade (The Division of AIDS Table for Grading the Severity of Adult and Pediatric Adverse Events, Corrected Version 2.1, July 2017. <https://rsc.niaid.nih.gov/clinical-research-sites/daids-adverse-event-grading-tables>), HIV status and arm. Serious adverse events (SAEs) are those AEs that result in one or more of the following outcomes:

- Death
- A life-threatening (i.e., an immediate threat to life) event
- Requires in-patient hospitalization or prolongation of an existing hospitalization
- A persistent or significant incapacity or substantial disruption of the ability to conduct normal life functions
- A congenital anomaly/birth defect
- A medically important event that may not be immediately life-threatening or result in death or hospitalization but may jeopardize the patient or may require intervention to prevent one of the other outcomes listed in the definition above

Examples of SAEs that can be expected to occur during this study include deaths (e.g., overdoses or other addiction-related deaths) and life-threatening events requiring intervention (e.g., overdose reversals).

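### Naloxone is on the opiate list for secondary objective 1d, so a urine positive only for naloxone is scored as opioid use

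*SAP*

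**What the plan says.** SAP Section 10, objective 1d, defines two binary urine outcomes, each analysed separately at weeks 26 and 52:

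- Opioid use: "Opioids (natural or synthetic) detected in urine samples for those retained at the week 26 and 52 visits".
- Polysubstance use: "Opioids (natural or synthetic) detected, along with stimulants (methamphetamine, cocaine), xylazine and/or benzodiazepines detected in urine samples".

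The same section then says what counts: "Opioids (natural or synthetic) include opiates, fentanyl and synthetic opioids". The opiate component is given analyte by analyte: "Opiate detection includes 6-mam, codeine, dihydrocodeine, heroin, hydrocodone, hydromorphone, morphine, morphine glucuronide naloxone, and normorphine". A comma is missing between morphine glucuronide and naloxone, but no other sensible reading is available.

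Both outcomes are analysed only in participants who gave urine at the visit. They use the Section 8 strategy, an identity-link GLM with arm and site.

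Section 5 sets out the laboratory evidence for MOUD: "biological detection of Buprenorphine (or Norbuprenorphine or Buprenorphine Glucuronide) or Methadone (or EDDP) will be performed". None of those analytes is on the opiate, fentanyl or synthetic opioid list in 1d.

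**The concern.** Naloxone blocks opioid receptors, and finding it in urine is not evidence that the participant used an opioid. It can get there through a buprenorphine product that contains it, or through treatment of an overdose. Because the 1d lists leave out every MOUD analyte named in Section 5, the outcome is evidently meant not to count treatment as use. Naloxone breaks that pattern.

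A participant could meet the MOUD success criterion and, because of the same product, be scored opioid-positive in 1d. The trial is designed to raise MOUD use in one arm, so this misclassification would not be balanced between arms. It would hide benefit among treated participants who had stopped using other opioids. The SAP plans no analysis that would reveal it.

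**Working it through.** **1. The rule as a programmer would apply it.** Naloxone is a listed opiate, opiates are part of opioids, and any detected opioid is a positive. A naloxone-only urine is therefore scored positive for opioid use. With a stimulant, xylazine or benzodiazepine it is also positive for polysubstance use. A urine that already contains another listed opioid is scored the same with or without naloxone on the list.

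**2. The plan's own figure.** The SAP gives no planning figure for 1d. The MOUD rates come from Section 2.5: 25% control, 40% intervention, 90% power, two-sided 5%, total 400. With unpooled variance, n per arm = (0.25×0.75 + 0.40×0.60) × (1.960 + 1.282)² / 0.15² ≈ 200, so the total is 400, as stated. The pooled formula gives 406. The rates and sample size are consistent.

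**3. Formula for the shift.** Let m be the MOUD share in an arm. Let s be the share of MOUD users with detectable naloxone, taken to be the same among those with no other listed opioid. Let q be the share of MOUD users with no other listed opioid. Assume s and q are equal in both arms and that naloxone comes only from MOUD.

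- False positives in an arm = m × s × q
- Shift in intervention minus control = (0.40 − 0.25) × s × q = 15 × s × q percentage points, against the intervention

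The values of s and q below are assumptions.

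| s | q | Control, false positives (%) | Intervention, false positives (%) | Shift (points) |
|---|---|---|---|---|
| any | near 0 | near 0 | near 0 | near 0 |
| 0.25 | 0.25 | 1.6 | 2.5 | 0.9 |
| 0.5 | 0.25 | 3.1 | 5.0 | 1.9 |
| 0.5 | 0.5 | 6.25 | 10.0 | 3.75 |
| 0.75 | 0.5 | 9.4 | 15.0 | 5.6 |
| 1 | 0.5 | 12.5 | 20.0 | 7.5 |

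**4. What such a shift does to a result.** Assume 95% opioid positivity off MOUD and 50% on MOUD (q = 0.5), with MOUD the only pathway.

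- True: control 0.75×0.95 + 0.25×0.50 = 83.75%; intervention 0.60×0.95 + 0.40×0.50 = 77.0%; difference −6.75 points.
- s = 0.5: 83.75 + 6.25 = 90.0% vs 77.0 + 10.0 = 87.0%; difference −3.0 points. Power at 200 per arm (two-proportion comparison without site) falls from about 40% to about 15%.
- s = 1: 96.25% vs 97.0%; difference +0.75 points.

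In this illustration the sign changes only if 7.5 × s exceeds 6.75, that is s > 0.90.

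**5. A limit of the input.** The 25% and 40% count missed visits as failures, whereas 1d uses only participants who gave urine. If 15% of each arm missed the visit (the threshold in Section 3.2) and every attender gave urine, the MOUD shares would be 25/0.85 = 29.4% and 40/0.85 = 47.1%. The factor 15 would become 15/0.85 = 17.6. The order of magnitude is unchanged.

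**The case against.** The wording has no good defence, but the size and direction of the bias can fairly be contested.

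- **The product share is unknown.** The SAP names buprenorphine and methadone, never a combined buprenorphine-naloxone product, and refers repeatedly to methadone clinics. Participants on methadone, or on buprenorphine alone, add nothing by this route. This stands, and is why s is left open.
- **Only naloxone-only urines change.** If most MOUD users remain positive for fentanyl or another listed opioid, q is near 0 and so is the shift. This stands.
- **Overdose reversal.** A reader might infer that naloxone given for reversal also counts against the intervention. Section 9.1 does expect reversals, but someone reversed from an opioid overdose will often be positive for that opioid anyway. If the intervention lowers overdoses (objective 1f), this route would favour it. Its direction by arm is unclear.
- **Reversal of the finding.** A reader might also infer that a large benefit could be turned into apparent harm. The documents do not support that as the expected case. Through MOUD alone at the planned rates, a 15-point benefit would need 100% positivity off MOUD and 0% on it (75% vs 60%). In the −6.75-point illustration, reversal needs more than 90% of all MOUD users to be naloxone-positive. Reversal at lower s requires a smaller true effect: at 90% positivity off MOUD and q = 0.25 the true difference is −2.25 points, the shift is 3.75 × s, and the sign changes above s = 0.6.
- **Scope.** The primary MOUD and PrEP outcomes, their models and the sample size are untouched.

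**Conclusion.** The definition is wrong as written: every naloxone-only urine is scored as opioid use, and the SAP contains no exemption. That part needs no assumption beyond naloxone being an antagonist.

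The size of the bias is uncertain. Through a combined buprenorphine-naloxone product, it runs against the arm with more MOUD use by 15 × s × q points at the planned rates. The range runs from near 0 to 3.75 points for s and q up to 0.5, and reaches 7.5 points at s = 1, q = 0.5. This rests on assumed s and q that are equal across arms and on the Section 2.5 MOUD rates holding among urine-givers. Dilution of a real effect is plausible; a reversed sign is an extreme case.

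The polysubstance outcome is affected only where a stimulant, xylazine or benzodiazepine is also present. This should be fixed, but it concerns two secondary outcomes at two visits and does not threaten the primary analysis.

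**What to change.** In SAP Section 10, objective 1d, for both outcomes at weeks 26 and 52:

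1. Delete naloxone from the opiate list.
2. Restore the comma after morphine glucuronide, so that any remaining text is unambiguous.
3. State that MOUD agents (buprenorphine, methadone and the metabolites named in Section 5) and naloxone do not count as opioid use.
4. Report naloxone detection descriptively by arm, without treating it as an outcome.

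The cost is a line or two of SAP wording and one derivation rule. No new data are needed if analyte-level urine results are kept, as the itemised lists suggest. The change should be made before the 1d outcomes are derived by arm.
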